**Vapotherm, Inc**  
**Hypercapnia Stabilization RCT NIPPV v HVNI**  
**Confidential**

**Phase 1 – Study Start/Setup & Patient Background**

Upon enrollment and randomization, the Study Start Phase will confirm inclusion criteria, record randomization to either study arm (HVNI or NIPPV), and will collect/record appropriate patient background, history, health, demographics, anthropometrics, and current respiratory therapies and respiratory status.

Appropriate Patient Background data will be collected (see below under Data Collection), including patient demographics (e.g. age, gender, ethnicity, race), anthropometrics (e.g. weight, height, BMI), COVID-19 status, and applicable medical history including a detailed focus on the patient's current respiratory status (LTOT user, positive-airway pressure therapy user, current respiratory therapy). Patient medication data will be recorded and tracked for this study. Patient data necessary for calculating the severity index score of BAP-65 will be recorded at this time.

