#### **Inclusion Criteria – *Selection of Inclusion***

1. Adults, 18 years or older with a known or suspected diagnosis of COPD
  - a. Suspected diagnosis of COPD defined as a history of smoking or significant second-hand smoke, plus clinical history of wheezing, chronic cough, bronchospasm, or exacerbations, and/or exposure with hypercapnia
2. Presentation with acute hypercapnic respiratory failure defined as:
  - a. Moderate to Severe patient baseline hypercarbia/hypercapnia, defined as a baseline PCO2 of 60 mmHg or higher (as measured by venous blood gas)
3. Venous pH of 7.0 – 7.35

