#### **Exclusion Criteria**

1. Severe metabolic derangements, e.g. suspected drug overdose, mixed acid/base disorder (bicarbonate at normal or above to be eligible)
2. Need for airway protection, e.g. neurologic disorder(s)
3. Primary condition of Congestive Heart Failure, e.g. Acute Severe Decompensated Heart Failure
4. Need for emergent intubation
5. Pneumonia diagnosis with significant infiltrate on chest x-ray that is clinically correlated with pneumonia
6. Inability to provide informed consent
7. Pregnancy
8. Known contraindication to perform procedures listed, or therapies described in the protocol
9. Respiratory arrest or significant respiratory depression on presentation
10. Significant nasal occlusion either unilateral or bilateral
11. Absence of spontaneous respiration or known contraindication to HVNI
12. Extreme agitation or uncooperativeness that would hinder either arm of randomized therapy
13. Determined by the clinician to be sufficiently unstable or unsuitable for this study

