**Vapotherm, Inc**  
**Hypercapnia Stabilization RCT NIPPV v HVNI**  
**Confidential**

This study will be conducted in an Emergency Department or Inpatient Critical Care setting, if applicable, where patient care and testing can be performed with appropriate supervision and staff training to maintain patient safety. In this acute-care setting study, participants may or may not decide to enroll after being consented. Patients may be excluded after randomization, as this study takes place in the ED or inpatient critical care unit and patients may need to be randomized and treated immediately to maintain patient safety. All respiratory interventions will be tracked during the study window for each patient.

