### **Sample Size:**

This trial will randomize subjects 1:1 to Vapotherm:NIPPV. A total sample size of 64 subjects (~32 per arm) randomized with endpoint data, and a one-sided alpha of 0.025 will provide at least 80% power to demonstrate non-inferiority. This sample size assumes a difference of 0.9 between treatment and control with standard deviation of 2.4 and 2.9 for treatment and control, respectively, and a non-inferiority margin of 1.0.

Allowing for up to 20% attrition, approximately 80 subjects (40 per arm) will be enrolled in order to achieve 64 subjects with an endpoint.

From Doshi et al, comparable moderate-to-severe hypercapnic respiratory distress patient data was analyzed, which informed this sample size calculation's assumed difference and standard deviations in treatment (HVNI) and control (NIPPV) for the modified Borg score.

Change in modified Borg over 4 hours	Mean	Standard Deviation
NIPPV arm (Control)	-3.208	2.431
HVNI arm (Treatment)	-4.143	2.931

The minimal clinically important difference (MCID) for modified Borg was informed from literature, as a difference value of 1.0.

**NOTE:** As this is an Emergency Department or inpatient acute care study, and treatment is often immediate due to need for maintaining patient safety, there is an expected patient dropout (i.e. incomplete or unusable subject number) of randomized & enrolled patients into this study. After presenting to the ED or inpatient acute care setting, should the patients be transferred to another area of the hospital, the study procedures will continue until complete.

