**Phase 2 – Baseline Characterization**

The baseline characterization will provide the initial clinical evaluation. Upon enrollment, randomization, and patient background collection, an venous blood gas sample will be drawn to establish the patient baseline at the time just prior to placing the patient on either of the study arm therapies (HVNI or NIPPV). Patient baseline for physiologic parameters (RR, HR, SpO2, BP, RPD) and venous blood gas parameters (PCO2, PO2, pH, bicarbonate, base excess,) will be collected at this time, prior to the initiation of the assigned/randomized therapy. A basic metabolic panel (BUN, CO2, Creatinine, Glucose, Chloride, Potassium, Sodium, Calcium) will also be collected at this time. For the RPD, the clinician will record patient scores. Patient Stability Index evaluation will be evaluated by clinicians and recorded at this time, described as follows: to assess patient clinical stability using a continuous VAS score on a scale from unable to speak, due to severe respiratory distress, up to speaks in full sentences without severe respiratory distress.

At baseline, only patient perception scores will take place. During the noted study phases, the clinician and the patient will complete VAS perception scores (annotated on 100mm line with an "X") for their randomized study arm (HVNI or NIPPV). Patient & Clinician Perception Assessment will be performed by the clinician or therapist performing or participating in the testing procedures. The Perception Assessments will be completed for each of the three endpoints for clinician assessment and the two endpoints for the patient assessment. For the patient perception/satisfaction these include: (1) relief of symptoms, and (2) comfort/tolerance. For the clinician perceptions these include: (1) expected/perceived patient outcomes, (2) patient comfort & tolerance, and (3) ease of use.

The assigned therapy per randomization will be implemented per the initial settings identified below, after which settings will be titrated per standard practice for optimal effect. Patients will be managed by routine care while study data is captured as per the timeline given in Table 1. Note: All decision making for intubation, treatment regimen, discharge, and disposition will be made per standard practice at each center using the judgment of the PI, Sub-I or their designee.

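### Inclusion criteria are confirmed after open-label randomisation, the qualifying blood gas is never named, and randomised patients may be excluded with no time limit or blinded review

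*Combined protocol and SAP*

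**What the plan says.** **Text that places eligibility after allocation**

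- Section VI, Phase 1: "Upon enrollment and randomization, the Study Start Phase will confirm inclusion criteria, record randomization to either study arm (HVNI or NIPPV". Confirmation of eligibility and recording of the arm are one step.
- Section III, inclusion criterion 2a: "Moderate to Severe patient baseline hypercarbia/hypercapnia, defined as a baseline" venous PCO2 of at least 60 mmHg. Criterion 3 sets a venous pH range. Exclusion 1 adds "bicarbonate at normal or above to be eligible".
- Section VI, Phase 2: "Upon enrollment, randomization, and patient background collection, an venous blood gas sample will be drawn to establish the patient baseline". The same paragraph places this gas just before the assigned therapy starts.
- Table 1 has no screening column. Blood gases first appear under Baseline Characterization.

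**Text that implies earlier screening**

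- Inclusion criterion 2 is framed in terms of the patient's presentation.
- Section IV randomises patients who present meeting the inclusion criteria, and says Study Start comes after screening and consent.
- Section VI (Screening, Enrollment, & Management) describes the selection criteria as already known when the patient presents.

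**Text that allows removal after randomisation**

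- Section IV: "Patients may be excluded after randomization". The reason given is that randomisation and treatment may have to be immediate.
- Section VI (Screening) gives an open-ended list of reasons for a randomised patient to be left out of the final study population: refusal of consent, meeting an exclusion criterion, incomplete data, and others.
- Section VIII names per-protocol and intention-to-treat analyses. It defines neither and makes neither primary.

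**The concern.** Two gaps combine.

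The first is an unresolved sequence. Criterion 2a relies on a baseline PCO2, and the only gas the protocol schedules as baseline comes after allocation. Suppose a patient has a PCO2 of 62 mmHg at presentation and 57 mmHg at Phase 2. The text does not settle whether that patient is eligible, and whoever decides already knows the arm.

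The second is the permission to exclude. It has no time limit, no restriction to facts that existed before randomisation, and no assessor blind to arm. Several exclusions are matters of judgement: pneumonia with a clinically correlated infiltrate (5), agitation or lack of cooperation (12), and the clinician's view that the patient is unstable or unsuitable (13). In an open-label trial, such judgements can be coloured by the arm and, if made late enough, by how the patient is doing.

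If poor responders were lost from the HVNI arm in this way, the comparison would move towards non-inferiority. A participant-flow diagram would disclose the losses but would not remove the bias.

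**Working it through.** **Sequence of steps**

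| Step | Relative to randomisation | Relative to therapy |
|---|---|---|
| Screening against criteria (Sections IV, VI) | Before, by implication | Before |
| Confirmation of inclusion (Phase 1) | After | Before |
| Baseline venous gas (Phase 2) | After | Just before |
| Exclusion permitted by Section IV | After, no limit | Not restricted |

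Only the last row can reach beyond the start of therapy. Section IV's own reason, the need to treat at once, contemplates treatment before exclusion.

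**The plan's own figure**

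Section V: "A total sample size of 64 subjects (~32 per arm) randomized with endpoint data, and a one-sided alpha of 0.025". The power claimed for this is 80% or more. The inputs: "This sample size assumes a difference of 0.9 between treatment and control with standard deviation of 2.4 and 2.9 for treatment and control, respectively". The margin is 1.0. The table there (change of −4.143 for HVNI, −3.208 for NIPPV) shows that the difference favours HVNI, so the distance from the margin is 0.9 + 1.0 = 1.9.

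- Normal approximation: n per arm = (1.960 + 0.842)² × (2.4² + 2.9²) / 1.9² = 7.85 × 14.17 / 3.61 = 30.8, so 31.
- With the t distribution, power is 79.0% at 31 per arm and 80.3% at 32. The stated 64 is reproduced.
- 64 / (1 − 0.20) = 80 enrolled, also reproduced.

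**Worst-case illustration**

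Assumptions: changes are normal, only the poorest HVNI responders are removed, and no NIPPV patient is removed selectively.

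1. Removing the lowest fraction p of a normal distribution raises its mean by SD × φ(z_p) / (1 − p). With SD 2.9:
   - p = 5%: 2.9 × 0.1031 / 0.95 = 0.31
   - p = 10%: 2.9 × 0.1755 / 0.90 = 0.57

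   With SD 2.4 the shifts are 0.26 and 0.47. Both SDs are shown because Section V's sentence and table assign them to opposite arms. The swap does not affect the sample size under 1:1 allocation.
2. SE = √((2.4² + 2.9²) / 32) = √0.443 = 0.665.
3. False non-inferiority rate when HVNI is truly worse by exactly the margin = Φ(shift / SE − 1.96):
   - shift 0: 2.5%
   - shift 0.3: Φ(0.451 − 1.960) = Φ(−1.509) = 6.6%
   - shift 0.5: Φ(0.751 − 1.960) = Φ(−1.209) = 11.3%

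A simulation under the same assumptions (40,000 runs, 40 randomised per arm, Welch t test) agrees. Ranges cover HVNI SDs of 2.4 and 2.9.

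| Worst HVNI responders removed, of 40 | Shift (Borg) | False non-inferiority rate |
|---|---|---|
| 0 | about 0 | about 2.4–2.5% |
| 1 | 0.13–0.17 | 4.2–5.0% |
| 2 | 0.24–0.30 | 6.5–8.3% |
| 4 | 0.45–0.55 | 13–17% |
| 8 | 0.81–1.0 | 31–44% |

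The last row equals the 20% attrition allowance applied to the HVNI arm.

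**The case against.** The strongest reply has five parts.

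- **Screening comes first.** Criterion 2 speaks of presentation, and Sections IV and VI place screening before randomisation. Phase 1 cannot confirm eligibility on a gas not drawn until Phase 2, so an earlier gas is implied. This stands against any reading that eligibility is established only after randomisation, which a reader might infer from Phase 1 alone. Post-randomisation confirmation may simply be a re-check. What remains is that no section names the qualifying gas or says that the re-check cannot reverse eligibility. Figure 1, the procedures flowchart, is not available to settle the order.
- **The Phase 2 gas precedes therapy.** This stands. A reader might infer that exclusion on this gas removes early poor responders, but no response exists at that point. Knowledge of the arm could still influence the decision.
- **Poor responders have their own category.** Section VI classes intolerance and inability to cooperate as treatment failure and requires failures to be recorded. Exclusion 12 refers to agitation that would hinder either therapy. This makes reclassification less natural, but the two definitions overlap and no rule says which prevails.
- **Intention-to-treat is named and exclusions are to be accounted for.** This is partial protection. Without a definition, the label does not override an explicit permission to exclude.
- **Some loss is unavoidable.** Written consent may follow randomisation, and a patient may then refuse. This stands, so simply deleting the Section IV sentence would not be enough.

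**Conclusion.** The point holds in a limited form. The documents are inconsistent about when eligibility is settled and silent on which gas settles it. They allow open-ended exclusion of randomised patients in an unblinded trial whose intention-to-treat set is undefined. Selection on response could arise only through that permission, combined with exclusions 5, 12 and 13, and not through the Phase 1 confirmation or the Phase 2 gas.

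The rise from 2.5% to about 6.6–11.3% is conditional on a shift of 0.3–0.5 Borg points and on wholly one-sided removal of the worst HVNI responders. It should not be read as the trial's expected error rate. Nothing in the documents gives a rate of differential exclusion or suggests that any site intends one. The number of patients who might cross 60 mmHg on a repeat gas cannot be derived from the documents either, and such crossings have no stated link to Borg change. The illustration shows only that, against a margin of 1.0 with about 32 per arm, a handful of selective exclusions would matter.

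The issue should be resolved in the text, because losses chosen with the arm known cannot be reliably repaired in analysis.

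**What to change.** 1. **Settle the sequence.** Reconcile the inclusion criteria, Section IV, and the Screening, Phase 1 and Phase 2 text of Section VI. All inclusion and exclusion criteria, including a dated and timed qualifying venous gas, should be confirmed and recorded before the arm is revealed. A one-page signed checklist would do. Add a screening column to Table 1.
2. **Limit the role of the Phase 2 gas.** State that it is a baseline measurement and does not reverse eligibility.
3. **Replace the Section IV permission.** All randomised patients stay in their assigned arm in the primary intention-to-treat analysis, which Section VIII should define. There are two exceptions: refusal or withdrawal of consent to use data, and ineligibility shown by facts that existed before randomisation and judged blind to arm and outcome.
4. **Account for the rest.** Anyone else later found ineligible is recorded as a protocol deviation (add an entry to Section XII) and kept in the analysis. Report all exclusions by arm, with reason and timing.

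The cost is protocol wording and a checklist. A qualifying gas before allocation is what the screening text already implies. A few ineligible patients will remain in the intention-to-treat set, and the per-protocol analysis can omit them. Retention need not cost power: with complete outcomes on all 80 randomised patients, power under the plan's own assumptions is 88.4% (t distribution, 40 per arm).

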**Phase 2 – Baseline Characterization**

The baseline characterization will provide the initial clinical evaluation. Upon enrollment, randomization, and patient background collection, an venous blood gas sample will be drawn to establish the patient baseline at the time just prior to placing the patient on either of the study arm therapies (HVNI or NIPPV). Patient baseline for physiologic parameters (RR, HR, SpO2, BP, RPD) and venous blood gas parameters (PCO2, PO2, pH, bicarbonate, base excess,) will be collected at this time, prior to the initiation of the assigned/randomized therapy. A basic metabolic panel (BUN, CO2, Creatinine, Glucose, Chloride, Potassium, Sodium, Calcium) will also be collected at this time. For the RPD, the clinician will record patient scores. Patient Stability Index evaluation will be evaluated by clinicians and recorded at this time, described as follows: to assess patient clinical stability using a continuous VAS score on a scale from unable to speak, due to severe respiratory distress, up to speaks in full sentences without severe respiratory distress.

At baseline, only patient perception scores will take place. During the noted study phases, the clinician and the patient will complete VAS perception scores (annotated on 100mm line with an "X") for their randomized study arm (HVNI or NIPPV). Patient & Clinician Perception Assessment will be performed by the clinician or therapist performing or participating in the testing procedures. The Perception Assessments will be completed for each of the three endpoints for clinician assessment and the two endpoints for the patient assessment. For the patient perception/satisfaction these include: (1) relief of symptoms, and (2) comfort/tolerance. For the clinician perceptions these include: (1) expected/perceived patient outcomes, (2) patient comfort & tolerance, and (3) ease of use.

The assigned therapy per randomization will be implemented per the initial settings identified below, after which settings will be titrated per standard practice for optimal effect. Patients will be managed by routine care while study data is captured as per the timeline given in Table 1. Note: All decision making for intubation, treatment regimen, discharge, and disposition will be made per standard practice at each center using the judgment of the PI, Sub-I or their designee.

**Initial Settings for Comparative Therapies – HVNI and NIPPV**

The initial settings in the two arms are designed as a standardization of usual medical treatment for the respective therapies and were devised to provide critical intervention and rapid abatement of both dyspnea and increased work of breathing. Once the patient has been placed upon the initial settings, the medical staff may, and should, manipulate and titrate the settings to optimize effectiveness and subject's tolerance. Overall

# Vapotherm, Inc

## Hypercapnia Stabilization RCT NIPPV v HVNI

Confidential

target should be to lower respiratory rate by 20% or below 24 br/min, while subsequently clinically stabilizing and reliving moderate-to-severe hypercapnic respiratory distress.

***HVNI will be initiated per the settings identified here***, after which settings will be titrated per standard practice for optimal effect. Patients will be fitted with a Vapotherm nasal cannula that will be applied by a respiratory therapist or other clinician skilled in management of HVNI (not to exceed 50% occlusion of the nares). When appropriate cannula are placed, the HVNI initial settings will be the following:  $\text{FiO}_2 = 0.50$  (unless the patient is receiving supplemental  $\text{O}_2$ , and then  $\text{FiO}_2$  will reflect amount of  $\text{O}_2$  patient is receiving provided that the  $\text{SpO}_2$  monitor reflects sufficient oxygenation), Flow = 30 L/min, and Temperature = 37°C. The flowrate can be decreased/increased as rapidly as necessary to optimize patient response and comfort, after a 5min acclimatization. Starting temperature will be 37°C; if patients find the gas temperature to be uncomfortable (warm), it can be lowered as necessary down to 33°C to enhance tolerance. The  $\text{FiO}_2$  will be set initially to approximate the likely previous dosage (if any) to initially to assure adequate oxygenation, but this should be adjusted (range 0.21 to 1.0) to maintain an  $\text{SpO}_2$  88-94%, per normal clinical management. If possible,  $\text{FiO}_2$  should be weaned to 0.30 or lower while maintaining  $\text{SpO}_2$  88-94%. NOTE: The flow rate is expected to be increased to the maximum rate of 40 L/min before a patient is removed from HVNI therapy.

***NIPPV will be initiated per the initial settings identified here***, after which settings will be titrated per standard practice for optimal effect. When patients are placed, the NIPPV initial settings will be the following: 12 cmH2O / 6 cmH2O (IPAP/EPAP), such that IPAP is 6 cmH2O above EPAP, with Backup Ventilation Rate = 0-4 breathes/min (lowest), and applied at the site's standard of care (SOC) for humidification (settings to be recorded). Patients will be fit with an oronasal mask using a fitting gauge that will be applied by a respiratory therapist or other clinician skilled in management of NIPPV. Initial pressures will be at low end of suggested range but can be increased as rapidly as necessary to alleviate respiratory distress. Targeted tidal volumes of 6-8 ml/kg ideal body weight will be the volume goal. If patients find pressures uncomfortably high/low, they can be adjusted as necessary by 1 to 2 cmH2O decrements to enhance tolerance. EPAP (PEEP) can also be adjusted upward as needed to reduce triggering effort (by counterbalancing auto-PEEP) or to improve oxygenation.  $\text{FiO}_2$  will be 0.50 initially to assure adequate oxygenation (unless the patient is receiving supplemental  $\text{O}_2$ , and then  $\text{FiO}_2$  will reflect amount of  $\text{O}_2$  patient is receiving provided that the  $\text{SpO}_2$  monitor reflects sufficient oxygenation), but should be adjusted promptly to maintain an  $\text{SpO}_2$  88-94%, per normal clinical management. If possible,  $\text{FiO}_2$  should be weaned to 0.30 or lower while maintaining  $\text{SpO}_2$  88-94%.

**Treatment failure will be defined as:**

1. **Failure to tolerate device** if the patient is unable to tolerate the mask, nasal prongs, air flow or pressure, has persisting asynchrony and is unable to cooperate with the therapy.
2. **Failure to oxygenate** if the modality is unable to sustain an  $\text{SpO}_2$  sat > 88 - 92% or  $\text{PaO}_2 > 60 - 65$  mmHg despite maximal treatment with  $\text{FiO}_2=100\%$  and optimal manipulations of flow rate and/or airway pressures, in spite of maximal settings per institutional standard.
3. **Failure to ventilate** if patients remain acutely hypercapnic and acidemic with lack of reduction in  $\text{PCO}_2$  or improvement in pH, in spite of maximal settings per institutional standard.
4. **Deteriorating medical status** correlating to worsening venous blood gases related to respiratory distress, manifested by worsening mental status or hemodynamics, manifested by hypotension

